4.6.2 Prohibited Concomitant Medications

Subjects are prohibited from receiving the following therapies during the Screening and Treatment Phase (including retreatment for post-complete response relapse) of this trial:

- Antineoplastic chemotherapy
- Immunotherapy not specified in this protocol
- Chemotherapy not specified in this protocol
- Investigational agents other than pembrolizumab
- Radiation therapy
 - Note: Radiation therapy to a symptomatic lesion or to the brain may be allowed as per the inclusion criteria, detailed in section 4.6.1, or at the investigator's discretion.
- Live vaccines within 30 days prior to the first dose of trial treatment and while participating in the trial. Examples of live vaccines include, but are not limited to, the following: measles, mumps, rubella, varicella/zoster, yellow fever, rabies, BCG, and typhoid vaccine.
- Systemic glucocorticoids for any purpose other than to modulate symptoms from an event of clinical interest of suspected immunologic etiology. The use of physiologic doses of corticosteroids may be approved after consultation with the Sponsor.

Subjects who, in the assessment by the investigator, require the use of any of the aforementioned treatments for clinical management should be removed from the trial. Subjects may receive other medications that the investigator deems to be medically necessary.

The Exclusion Criteria describes other medications that are prohibited in this trial.

There are no prohibited therapies during the Post-Treatment Follow-up Phase.

4.7 Rescue Medications & Supportive Care

4.7.1 Supportive Care Guidelines

Subjects should receive appropriate supportive care measures as deemed necessary by the treating investigator. Suggested supportive care measures for the management of adverse events with potential immunologic etiology are outlined below. Where appropriate, these guidelines include the use of oral or intravenous treatment with corticosteroids as well as additional anti-inflammatory agents if symptoms do not improve with administration of corticosteroids. Note that several courses of steroid tapering may be necessary as symptoms may worsen when the steroid dose is decreased. For each disorder, attempts should be made to rule out other causes such as metastatic disease or bacterial or viral infection, which might require additional supportive care. The treatment guidelines are intended to be applied when the investigator determines the events to be related to pembrolizumab.

Note: if after the evaluation the event is determined not to be related, the investigator does not need to follow the treatment guidance (as outlined below). Refer to Section 5.2.1 for dose modification.

It may be necessary to perform conditional procedures such as bronchoscopy, endoscopy, or skin photography as part of evaluation of the event.

• Pneumonitis:

- For Grade 2 events, treat with systemic corticosteroids. When symptoms improve to Grade 1 or less, steroid taper should be started and continued over no less than 4 weeks.
- For Grade 3-4 events, immediately treat with intravenous steroids.
 Administer additional anti-inflammatory measures, as needed.
- Add prophylactic antibiotics for opportunistic infections in the case of prolonged steroid administration.

• Diarrhea/Colitis:

Subjects should be carefully monitored for signs and symptoms of enterocolitis (such as diarrhea, abdominal pain, blood or mucus in stool, with or without fever) and of bowel perforation (such as peritoneal signs and ileus).

- O All subjects who experience diarrhea/colitis should be advised to drink liberal quantities of clear fluids. If sufficient oral fluid intake is not feasible, fluid and electrolytes should be substituted via IV infusion. For Grade 2 or higher diarrhea, consider GI consultation and endoscopy to confirm or rule out colitis.
- o For Grade 2 diarrhea/colitis, administer oral corticosteroids.

- For Grade 3 or 4 diarrhea/colitis, treat with intravenous steroids followed by high dose oral steroids.
- O When symptoms improve to Grade 1 or less, steroid taper should be started and continued over no less than 4 weeks.
- Type 1 diabetes mellitus (if new onset, including diabetic ketoacidosis [DKA]) or ≥ Grade 3 Hyperglycemia, if associated with ketosis (ketonuria) or metabolic acidosis (DKA)
 - o For **T1DM** or **Grade 3-4** Hyperglycemia
 - Insulin replacement therapy is recommended for Type I diabetes mellitus and for Grade 3-4 hyperglycemia associated with metabolic acidosis or ketonuria.
 - Evaluate patients with serum glucose and a metabolic panel, urine ketones, glycosylated hemoglobin, and C-peptide.

Hypophysitis:

- o For Grade 2 events, treat with corticosteroids. When symptoms improve to Grade 1 or less, steroid taper should be started and continued over no less than 4 weeks. Replacement of appropriate hormones may be required as the steroid dose is tapered.
- o For **Grade 3-4** events, treat with an initial dose of IV corticosteroids followed by oral corticosteroids. When symptoms improve to Grade 1 or less, steroid taper should be started and continued over no less than 4 weeks. Replacement of appropriate hormones may be required as the steroid dose is tapered.

• Hyperthyroidism or Hypothyroidism:

Thyroid disorders can occur at any time during treatment. Monitor patients for changes in thyroid function (at the start of treatment, periodically during treatment, and as indicated based on clinical evaluation) and for clinical signs and symptoms of thyroid disorders.

- o **Grade 2** hyperthyroidism events (and **Grade 2-4** hypothyroidism):
 - In hyperthyroidism, non-selective beta-blockers (e.g. propranolol) are suggested as initial therapy.
 - In hypothyroidism, thyroid hormone replacement therapy, with levothyroxine or liothyroinine, is indicated per standard of care.
- Grade 3-4 hyperthyroidism
 - Treat with an initial dose of IV corticosteroid followed by oral corticosteroids. When symptoms improve to Grade 1 or less, steroid taper should be started and continued over no less than 4 weeks. Replacement of appropriate hormones may be required as the steroid dose is tapered.

• Hepatic:

- o For **Grade 2** events, monitor liver function tests more frequently until returned to baseline values (consider weekly).
 - Treat with IV or oral corticosteroids
- o For **Grade 3-4** events, treat with intravenous corticosteroids for 24 to 48 hours.
- When symptoms improve to Grade 1 or less, a steroid taper should be started and continued over no less than 4 weeks.

• Renal Failure or Nephritis:

- o For Grade 2 events, treat with corticosteroids.
- o For **Grade 3-4** events, treat with systemic corticosteroids.
- o When symptoms improve to Grade 1 or less, steroid taper should be started and continued over no less than 4 weeks.
- Management of Infusion Reactions: Signs and symptoms usually develop during or shortly after drug infusion and generally resolve completely within 24 hours of completion of infusion.

Table 6 below shows treatment guidelines for subjects who experience an infusion reaction associated with administration of pembrolizumab (MK-3475).

Table 6. Infusion Reaction Treatment Guidelines

NCI CTCAE Grade	Treatment	Premedication at subsequent dosing
Grade 1 Mild reaction; infusion interruption not indicated; intervention not indicated	Increase monitoring of vital signs as medically indicated until the subject is deemed medically stable in the opinion of the investigator.	None
Grade 2 Requires infusion interruption but responds promptly to symptomatic treatment (e.g., antihistamines, NSAIDS, narcotics, IV fluids); prophylactic medications indicated for < =24 hrs	Stop Infusion and monitor symptoms. Additional appropriate medical therapy may include but is not limited to: IV fluids Antihistamines NSAIDS Acetaminophen Narcotics Increase monitoring of vital signs as medically indicated until the subject is deemed medically stable in the opinion of the investigator. If symptoms resolve within one hour of stopping drug infusion, the infusion may be restarted at 50% of the original infusion rate (e.g., from 100 mL/hr to 50 mL/hr). Otherwise dosing will be held until symptoms resolve and the subject should be premedicated for the next scheduled dose. Subjects who develop Grade 2 toxicity despite adequate premedication should be permanently discontinued from further trial treatment administration.	Subject may be premedicated 1.5h (± 30 minutes) prior to infusion of pembrolizumab (MK-3475) with: Diphenhydramine 50 mg po (or equivalent dose of antihistamine). Acetaminophen 500-1000 mg po (or equivalent dose of antipyretic).
Grades 3 or 4	Stop Infusion.	No subsequent dosing
Grade 3: Prolonged (i.e., not rapidly responsive to symptomatic medication and/or brief interruption of infusion); recurrence of symptoms following	Additional appropriate medical therapy may include but is not limited to: IV fluids Antihistamines NSAIDS Acetaminophen Narcotics	

NCI CTCAE Grade	Treatment	Premedication at subsequent dosing
initial improvement; hospitalization	Oxygen	
indicated for other clinical sequelae	Pressors	
(e.g., renal impairment, pulmonary	Corticosteroids	
infiltrates)	Epinephrine	
Grade 4: Life-threatening; pressor or ventilatory support indicated	Increase monitoring of vital signs as medically indicated until the subject is deemed medically stable in the opinion of the investigator. Hospitalization may be indicated. Subject is permanently discontinued from further trial treatment administration.	
Appropriate resuscitation equipment she administration.	ould be available in the room and a physician readil	y available during the period of drug

4.8 Diet/Activity/Other Considerations

4.8.1 Diet

Subjects should maintain a normal diet unless modifications are required to manage an AE such as diarrhea, nausea or vomiting.

4.8.2 Contraception

Pembrolizumab may have adverse effects on a fetus in utero. Furthermore, it is not known if pembrolizumab has transient adverse effects on the composition of sperm.

For this trial, male subjects will be considered to be of non-reproductive potential if they have azoospermia (whether due to having had a vasectomy or due to an underlying medical condition).

Female subjects will be considered of non-reproductive potential if they are either:

(1) postmenopausal (defined as at least 12 months with no menses without an alternative medical cause; in women < 45 years of age a high follicle stimulating hormone (FSH) level in the postmenopausal range may be used to confirm a post-menopausal state in women not using hormonal contraception or hormonal replacement therapy. In the absence of 12 months of amenorrhea, a single FSH measurement is insufficient.);

OR

(2) have had a hysterectomy and/or bilateral oophorectomy, bilateral salpingectomy or bilateral tubal ligation/occlusion, at least 6 weeks prior to screening;

OR

(3) has a congenital or acquired condition that prevents childbearing.

Female and male subjects of reproductive potential must agree to avoid becoming pregnant or impregnating a partner, respectively, while receiving study drug and for 120 days after the last dose of study drug by complying with one of the following:

(1) practice abstinence[†] from heterosexual activity;

OR

(2) use (or have their partner use) acceptable contraception during heterosexual activity.

Acceptable methods of contraception are[‡]:

Single method (one of the following is acceptable):

- intrauterine device (IUD)
- vasectomy of a female subject's male partner
- contraceptive rod implanted into the skin

Combination method (requires use of two of the following):

- diaphragm with spermicide (cannot be used in conjunction with cervical cap/spermicide)
- cervical cap with spermicide (nulliparous women only)
- contraceptive sponge (nulliparous women only)
- male condom or female condom (cannot be used together)
- hormonal contraceptive: oral contraceptive pill (estrogen/progestin pill or progestinonly pill), contraceptive skin patch, vaginal contraceptive ring, or subcutaneous contraceptive injection

†Abstinence (relative to heterosexual activity) can be used as the sole method of contraception if it is consistently employed as the subject's preferred and usual lifestyle and if considered acceptable by local regulatory agencies and ERCs/IRBs. Periodic abstinence (e.g., calendar, ovulation, sympto-thermal, post-ovulation methods, etc.) and withdrawal are not acceptable methods of contraception.

‡If a contraceptive method listed above is restricted by local regulations/guidelines, then it does not qualify as an acceptable method of contraception for subjects participating at sites in this country/region.

Subjects should be informed that taking the study medication may involve unknown risks to the fetus (unborn baby) if pregnancy were to occur during the study. In order to participate in the study subjects of childbearing potential must adhere to the contraception requirement (described above) from the day of study medication initiation (or 14 days prior to the initiation of study medication for oral contraception) throughout the study period up to 120 days after the last dose of trial therapy. If there is any question that a subject of childbearing potential will not reliably comply with the requirements for contraception, that subject should not be entered into the study.

4.8.3 Use in Pregnancy

If a subject inadvertently becomes pregnant while on treatment with pembrolizumab, the subject will immediately be removed from the study. The site will contact the subject at least monthly and document the subject's status until the pregnancy has been completed or terminated. The outcome of the pregnancy will be reported to the Sponsor and to Merck without delay and within 24 hours to the Sponsor and within 2 working days to Merck if the outcome is a serious adverse experience (e.g., death, abortion, congenital anomaly, or other disabling or life-threatening complication to the mother or newborn).

The study investigator will make every effort to obtain permission to follow the outcome of the pregnancy and report the condition of the fetus or newborn to the Sponsor. If a male subject impregnates his female partner the study personnel at the site must be informed immediately and the pregnancy reported to the Sponsor and to Merck and followed as described above and in Section 6.2.2.

4.8.4 Use in Nursing Women

It is unknown whether pembrolizumab is excreted in human milk. Since many drugs are excreted in human milk, and because of the potential for serious adverse reactions in the nursing infant, subjects who are breast-feeding are not eligible for enrollment.

4.9 Subject Withdrawal/Discontinuation Criteria

Subjects may withdraw consent at any time for any reason or be dropped from the trial at the discretion of the investigator should any untoward effect occur. In addition, a subject may be withdrawn by the investigator or the Sponsor if enrollment into the trial is inappropriate, the trial plan is violated, or for administrative and/or other safety reasons. Specific details regarding discontinuation or withdrawal are provided in Section 7.1.4 – Other Procedures.

A subject must be discontinued from the trial for any of the following reasons:

- The subject or legal representative (such as a parent or legal guardian) withdraws consent.
- CNS progression (as detailed in Table 8)
- Unacceptable adverse experiences as described in Section 6.2.
- Intercurrent illness that prevents further administration of treatment
- Investigator's decision to withdraw the subject
- The subject has a confirmed positive serum pregnancy test
- Noncompliance with trial treatment or procedure requirements
- The subject is lost to follow-up

• Completed 24 months of uninterrupted treatment with pembrolizumab or 35 administrations of study medication, whichever is later.

Note: 24 months of study medication is calculated from the date of first dose. Subjects who stop pembrolizumab after 24 months may be eligible for up to one year of additional study treatment if they progress after stopping study treatment.

Administrative reasons

The End of Treatment and Follow-up visit procedures are listed in Section 5.0 (Trial Flow Chart). After the end of treatment, each subject will be followed for 30 days for adverse event monitoring (serious adverse events will be collected for 90 days after the end of treatment as described in Section 6.1.5.1). Subjects who discontinue for reasons other than progressive disease will have post-treatment follow-up for disease status until disease progression, initiating a non-study cancer treatment, withdrawing consent or becoming lost to follow-up. After documented disease progression each subject will be followed by telephone for overall survival until death, withdrawal of consent, or the end of the study, whichever occurs first.

4.9.1 Discontinuation of Study Therapy after CR

Discontinuation of treatment may be considered for subjects who have attained a confirmed CR that have been treated for at least 24 weeks with pembrolizumab and had at least two treatments with pembrolizumab beyond the date when the initial CR was declared.

4.9.2 Subject Replacement Strategy

A subject who discontinues from the trial will not be replaced.

4.10 Clinical Criteria for Early Trial Termination

Early trial termination will be the result of the criteria specified below:

- 1. Quality or quantity of data recording is inaccurate or incomplete
- 2. Poor adherence to protocol and regulatory requirements
- 3. Incidence or severity of adverse drug reaction in this or other studies indicates a potential health hazard to subjects
- 4. Plans to modify or discontinue the development of the study drug

In the event of Merck decision to no longer supply study drug, ample notification will be provided so that appropriate adjustments to subject treatment can be made.

5.0 TRIAL FLOW CHART

Table 7: Study Flow Chart

Trial Period:	Screenin g Phase	Treatment Cycles ^a						End of Treatment		Post-Treatment			
	Study Screening					showi	s 5+ on ng clin	nical b	enefit.				Survival
Treatment Cycle/Title:	(Visit 1)	1	2	3	4	5	6	7	8	Discon ⁹	Safety Follow-up	Follow Up Visits	Follow- Up
Scheduling Window (Days):	-28 to -1	± 3 ⁸	± 3	± 3	± 3	± 3	± 3	± 3	± 3	At time of discon	30 days post discon	Every 6-9 weeks post discon	Every 12 weeks
Administrative Procedures													
Informed Consent	X												
Inclusion/Exclusion Criteria	X												
Demographics and Medical History	X												
Prior and Concomitant Medication Review	X	X	X	X	X	X	X	X	X	X	X	X	
Post-study anticancer therapy status	X									X	X	X	
Survival Status													X
Clinical Procedures/Assessments													
Review Adverse Events	X	X	X	X	X	X	X	X	X	X	X	X	
Full Physical Examination	X									X			
Directed Physical Examination		X	X	X	X	X	X	X	X				
Vital Signs, Weight	X	X	X	X	X	X	X	X	X	X			
Oxygen saturation	X	X	X	X	X	X	X	X	X	X			
ECOG Performance Status	X	X	X	X	X	X	X	X	X	X			
Pembrolizumab Administration		X	X	X	X	X	X	X	X				
Laboratory Procedures/Assessments: anal	ysis perforr	ned by	LOCA	L labo	ratory								
Pregnancy Test – Urine or Serum β -HCG ¹	X	X	X	X	X	X	X	X	X	X	X		
PT/INR and aPTT	X												
CBC with Differential	X	X	X	X	X	X	X	X	X	X	X		

Trial Period:	Screenin g Phase	Treatment Cycles ^a							End of T	reatment	Post-Treatment		
	Study Screening					showi	s 5+ on ng clin continue	nical b	enefit.		G. C.	F 11 H	Survival
Treatment Cycle/Title:	(Visit 1)	1	2	3	4	5	6	7	8	Discon ⁹	Safety Follow-up	Follow Up Visits	Follow- Up
Scheduling Window (Days):	-28 to -1	± 3 ⁸	± 3	± 3	± 3	± 3	± 3	± 3	± 3	At time of discon	30 days post discon	Every 6-9 weeks post discon	Every 12 weeks
Comprehensive Serum Chemistry Panel	X	X	X	X	X	X	X	X	X	X	X		
Urinalysis	X												
TSH ²	X		X		X		X		X	X			
Hepatitis B, C, HIV	X												
Efficacy Measurements													
MRI Brain and Full-spine with contrast	X			X ³		X^3				X^3		X^4	
CT chest/abdomen/pelvis with contrast	X			X ³		X^3				X^3		X^4	
Tumor Biopsies/Archival Tissue Collection	ı/Correlativ	e Studi	ies Blo	od									
Archival Tissue Collection ⁵	X												
Blood collection for Genomics	X			X		X				X			
Blood collection for Immune correlates	X			X		X				X			
CSF sample acquisition ⁶	X			X		X ⁷				X^7			
CSF sample correlates	X			X		X^7				X^7			

¹ In women of childbearing potential only. If urine test is positive or not evaluable, serum test is required

² T3 and Free T4 will be done if TSH is abnormal

³ Restaging with MRI Brain and CT scan should be completed anytime between cycle 2 and 3, and anytime between cycle 4 and 5. In patients who only received the planned 4 doses of therapy, this is replaced with the end of treatment MRI and CT, which should be done within +/-4 weeks of the last dose of therapy

⁴Re-imaging in follow-up will be completed every 9 weeks +/- 7 days or at the treating physician's discretion.

⁵ In patients were tissue is available

⁶ Via lumbar puncture or use of a CSF-device if available

⁷ In patients who receive +4 treatments, a CSF sample will be taken prior to the 5th treatment. In patients who only received the planned 4 doses of therapy, the second CSF sample and blood collection for both genomic and immune correlates is an end-of-treatment sample and should be taken within 2 weeks of the last dose of therapy.

⁸Screening labs may be used for Cycle 1 Day 1 if they are done within 3 days of C1D1.

of the end of treatment visit will be considered to be performed at the date of the last dose of therapy, if the study participant goes on to receive a new anti-cancer agent within 30 days of last study therapy.

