4.3 Trial Treatments

The treatment to be used in this trial is outlined below in Table 4:

Table 4: Trial Treatment

Drug	Dose/Potency	Dose	Route of	Regimen/Treatment Period	Use
		Frequency	Administration		
Pembrolizumab	200 mg	Q3W	IV infusion	Day 1 of each 3 week cycle	Experimental

Trial treatment should begin on the day of registration or as close as possible to the date on which treatment is allocated/assigned.

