6.1.2.7.2. Tumor Imaging During the Trial

The first on study imaging assessment should be performed anytime between cycle 2 and 3 of planned therapy, and the second set of imaging should be performed anytime between cycle 4 and 5. In patients who only receive the planned 4 doses of therapy, this is replaced with the end of treatment MRI and CT, which should be done within 2 weeks of the last dose of therapy. Subsequent tumor imaging should be performed Q9W (±7 days) or more frequently if clinically indicated until PD. Imaging should not be delayed for delays in cycle starts or extension of pembrolizumab cycle intervals.

To assess radiologic response in the CNS, there are no standard radiologic response criteria for LMD on CT or MRI. The RANO group has proposed criteria for measuring BM⁷⁷, but not for LMD. From an extensive review of published literature of clinical trials and assessments of LMD in the modern MRI era^{33,78}, we propose using a radiologic cut-off of 3mm for measurable disease in the neuro-axis by gadolinium-enhanced MRI imaging of the brain and total spine including T1- weighted, T2-weighted, fluid attenuated inversion recovery and post-gadolinium sequences.

To assess for response outside of the CNS, per RECIST 1.1, partial or complete response should be confirmed by a repeat tumor imaging assessment not less than 4 weeks from the date the response was first documented. The tumor imaging for confirmation of response may be performed at the earliest 4 weeks after the first indication of response, or at the next scheduled tumor imaging (i.e. 9 weeks later), whichever is clinically indicated. Subjects will then return to regular scheduled imaging Q9W, starting with the next scheduled imaging time point. Subjects who obtain a confirmation imaging assessment do not need to undergo scheduled tumor imaging if it is < 4 weeks later and may wait until the next scheduled imaging time point.

Per irRECIST, if radiologic imaging identifies PD, tumor assessment should be repeated ≥ 4 weeks later in order to confirm PD with the option of continuing treatment while awaiting radiologic confirmation of progression. Subjects who obtain confirmation tumor imaging do not need to undergo scheduled tumor imaging if it is < 4 weeks later and may wait until the next scheduled imaging time point if clinically stable.

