6.1.2.7.3. End of Treatment and Follow-up Tumor Imaging

In subjects who discontinue trial treatment, tumor imaging should be performed at the time of treatment discontinuation (\pm 4 week window). If a previous CT scan for body imaging and MRI for CNS imaging was obtained within 4 weeks prior to the date of discontinuation, then a scan at treatment discontinuation isn't mandatory.

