6.1.2.8.3. CSF Sample collection

Patients will undergo a lumbar puncture using routine clinical care procedures to collect up to 10-15cc of CSF for research purposes, after routine clinical CSF is obtained. In patients with a CSF-access device such as an Ommaya reservoir or shunt reservoir, the study team may use this device to obtain CSF as an alternative to lumbar puncture. A CSF sample will be obtained during screening to obtain a "baseline" sample, and assess for eligibility based on CSF cytology. In patients who proceed with the study, repeat CSF samples will be obtained prior to administration of cycle 3 of therapy and 2-3 weeks after administration of cycle 4 (if last treatment, as end-of-treatment sample) or prior to cycle 5, if the patient is planned to receive cycle 5. The maximum number of lumbar punctures from an individual patient is four. In order to safely complete an LP for the acquisition of a CSF sample, patients must:

- a) Have an ECOG performance status < 2
- b) Have normal laboratory criteria as defined below:
- -Platelets >100,000/mcL[SEP]
- -PTT above institutional limits
- -INR above institutional limits
- c) No clinical or radiographic evidence of elevated intracranial pressure (such as papilledema, obstructive hydrocephalus, or signs of herniation).
- d) Not be taking blood-thinning products such as clopidogrel, low-molecular weight heparin, or coumadin.
- 5) For patients undergoing an LP, no history of LP complication such as hematoma, infection, herniation, or blood patch, and a complicated LP procedure in the past.

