7. STATISTICAL ANALYSIS PLAN

7.1. Statistical Analysis Plan Summary

Key elements of the statistical plan are summarized in Table 12 below. A comprehensive plan is detailed in section 7.2

Table 12: Statistical Overview

Study Design Overview	Open-label, single arm phase II study of pembrolizumab in patients with advanced solid tumors with leptomeningeal carcinomatosis (LMD)
Treatment Assignment	pembrolizumab 200mg Q3W
Analysis Population	Eligible patients who receive at least one dose of pembrolizumab
Primary Endpoint	CNS response at 12 weeks based on either radiologic, cytologic or clinical evidence
Statistical Methods for Key Efficacy Analyses	The proportion of CNS response and associated 95% exact confidence interval will be provided
Statistical Methods for	Descriptive analysis based on Clopper-Pearson's exact binomial confidence interval method.
Key Safety Analyses	
Multiplicity	N.A.
Sample Size and Power	No formal statistical inference will be provided. The proposed sample size will provide appropriate estimation precision for the primary efficacy endpoint.

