7.2. Statistical Analysis Plan

7.2.1 Statistical Plan

This is an open-label phase II study aimed at establishing the efficacy of single agent pembrolizumab, at the FDA-approved dose of 200mg every 3 weeks, in patients with solid

tumors and LMD. The primary endpoint will be CNS response at 12 weeks/after 4 cycles of therapy. The sample size is calculated with Clopper-Pearson's exact binomial confidence interval method. With 16 analyzable patients, defined as eligible patients who receive at least one dose of pembrolizumab, we determine that we will have an appropriate level of estimation accuracy for the first study of this experimental regimen. The following table summarizes the two-sided 90% exact confidence interval for different observed CNS response rate. Guarding against a 10% rate of patients either being ineligible or dropping out, the final sample size is 18 patients. If a higher rate of ineligible and drop-out rate is observed during the study conduct, the protocol may be amended to ensure at least 16 analyzable cases.

No. of patients with CNS response (%)	90% Confidence Interval for Observed CNS Response Rate (N=16)	
	Lower (%)	Upper (%)
1 (6.3%)	0.3	26.4
2 (12.5%)	2.3	34.4
3 (18.8%)	5.3	41.7
4 (25%)	9.0	48.4
5 (31.3%)	13.2	54.8
6 (37.5%)	17.8	60.1

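### For patients who stop after four doses, the MRI and CSF behind the 12-week primary endpoint have conflicting windows: one admits a scan before dose 4, others close before week 12

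*Combined protocol and SAP*

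**What the plan says.** Two places fix the time of the primary endpoint. Table 12 (section 7.1) has "CNS response at 12 weeks based on either radiologic, cytologic or clinical evidence", and section 7.2.1 has "The primary endpoint will be CNS response at 12 weeks/after 4 cycles of therapy". Section 2.1 likewise places the response MRI and CSF after the second and fourth cycles. Sections 4.1.5.1.1 and 7.2.4, which define response, carry no time point. No section says which scan, CSF sample or examination is the 12-week assessment.

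Dosing is on "Day 1 of each 3 week cycle". Four doses are planned, and further cycles are for patients who benefit. For those who continue, Table 7 footnote 3 and section 6.1.2.7.2 agree that the second restaging falls between cycles 4 and 5. For those who stop at four doses, an end-of-treatment assessment takes its place, and its timing depends on where one looks:

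- MRI, Table 7 footnote 3: "which should be done within +/-4 weeks of the last dose of therapy".
- MRI, section 6.1.2.7.2: "which should be done within 2 weeks of the last dose of therapy".
- MRI, section 6.1.2.7.3: a 4-week window either side of discontinuation, with no scan required if one "was obtained within 4 weeks prior to the date of discontinuation".
- CSF, Table 7 footnote 7: "is an end-of-treatment sample and should be taken within 2 weeks of the last dose of therapy".
- CSF, section 6.1.2.8.3: "2-3 weeks after administration of cycle 4".

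**The concern.** These assessments supply the radiologic and cytologic parts of the primary endpoint for every patient who follows the planned four-dose course. If their windows disagree, sites can all comply and still measure response at different times. The wide MRI window starts before dose 4, so a scan that cannot show response after four cycles is still in window. The narrow windows end before the 12 weeks that the SAP names. Since section 7.2.4 does not name the assessment that counts, the analyst has no written rule for sorting this out afterwards. The reported proportion could then mix early response with response at week 12, and an early response later lost, or followed by death, could be counted as a 12-week response.

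**Working it through.** **Inputs.** Three-week cycles (section 4.3, Table 4); four planned doses (section 2.1); the five windows listed above; first restaging between cycles 2 and 3 (footnote 3 and section 6.1.2.7.2); endpoint at 12 weeks (sections 7.1 and 7.2.1). Doses are assumed to be on schedule.

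**Calendar.** Doses fall on days 1, 22, 43 and 64. Week 12 is day 1 + 84 = 85, which is 3 weeks after dose 4.

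| Assessment | Rule | Days | Reaches day 85? |
|---|---|---|---|
| First restaging MRI | between cycles 2 and 3 | 22-43 | no |
| End-of-treatment MRI, footnote 3 | 64 ± 28 | 36-92 | yes, but opens 28 days before dose 4 |
| End-of-treatment MRI, 6.1.2.7.2 | 64 + 14 | 64-78 | no |
| End-of-treatment CSF, footnote 7 | 64 + 14 | 64-78 | no |
| End-of-treatment CSF, 6.1.2.8.3 | 64 + 14 to 64 + 21 | 78-85 | yes |

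**Overlaps.** The footnote 3 window and the first restaging window share days 36-43 (weeks 5-6). The two CSF windows share day 78 only. If the 2-week rules are read as two-sided they open on day 50 (64 - 14), but still close on day 78. If dose 4 is given 3 days late, as section 4.3.2 allows, they close on day 81, still 4 days short of week 12.

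**The waiver in 6.1.2.7.3.** It looks back 28 days from discontinuation. If discontinuation is dated to dose 4, it reaches 64 - 28 = day 36. If it is dated to day 85, when a fifth dose would have been due, it reaches 85 - 28 = day 57. That is clear of the first restaging window but still a week before dose 4.

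**Later imaging.** Table 7 puts follow-up visits every 6-9 weeks after discontinuation. Counted from the earliest date possible for these patients, day 64, that gives days 106-127 (64 + 42 to 64 + 63), or weeks 15-18. Footnote 4 allows a scan at the physician's discretion, but nothing requires one at week 12.

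**Confirmatory CSF.** Cytologic response needs two consecutive negatives, with the second sample 3 weeks after the first (section 2.1). A first negative at weeks 11-12 is confirmed at weeks 14-15, past the endpoint time under any of these windows.

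**Size.** Clopper-Pearson limits at 90% for N = 16 reproduce the relevant rows of the table in section 7.2.1: 4/16 gives 9.0-48.4% and 5/16 gives 13.2-54.8%. One reclassified patient moves the estimate from the first row to the second. At the 95% level named in Table 12, the same step is from 7.3-52.4% to 11.0-58.7%.

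For scale on deaths, take the 3-6 month median survival in section 4.1.4.5 as 13-26 weeks and assume exponential survival. Among patients alive at dose 4 (week 9), the share dying by week 12 is 1 - 0.5^(3/26) = 8% to 1 - 0.5^(3/13) = 15%.

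**The case against.** The strongest reply is that the intent is clear. Footnote 3 asks for two separate restagings, and the end-of-treatment scan replaces only the second. Section 2.1 wants MRI after two and after four cycles, and section 7.2.1 ties the endpoint to four cycles. A scan before dose 3 or dose 4 satisfies none of that. This stands, and it limits the point. A reader might infer that a week 5-6 scan will stand in for the 12-week endpoint, or that following the flow chart leaves no MRI after dose 4. The documents do not support either as a consequence of the plan. The substitution is a risk of reading the 4-week limit literally. The waiver reaches weeks 5-6 only if discontinuation is dated to the last dose; Table 7's final footnote and section 6.1.4.1 date the end-of-treatment visit that way only when a new anti-cancer agent starts within 30 days. Follow-up MRI also continues for patients without CNS progression or new therapy, though not at week 12.

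Three further replies also carry weight. Patients who benefit may continue, and their imaging windows agree, so likely responders are the least exposed. Day 78 is only a week from day 85, and section 7.2.1 treats 12 weeks and four cycles as one nominal time. Finally, Table 12 plans no formal inference, so no decision threshold is at risk.

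A reader might also measure deaths over weeks 6-12, which on the same assumption gives 1 - 0.5^(6/26) = 15% to 1 - 0.5^(6/13) = 27%. That is the wrong risk set, because a four-dose patient must be alive at week 9. Nor is the endpoint without a time point: sections 7.1 and 7.2.1 supply one, although 4.1.5.1.1 and 7.2.4 do not.

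None of this removes the conflict. Two MRI rules and two CSF rules apply to the same patients, and no rule says which prevails.

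**Conclusion.** The point holds as a contradiction in the timing of the assessments that feed the primary endpoint, confined to patients who stop after the four planned doses. One MRI rule opens on day 36, four weeks before dose 4. The other closes on day 78, one week before week 12. The two CSF rules meet on a single day. This is more than missing detail, because a stated rule accepts a scan that the endpoint definition excludes.

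The day counts assume on-schedule dosing; a longer delay to dose 4 would move the 2-week limits towards or past day 85. The effect on the estimate cannot be derived from the documents, which do not show how many patients would be affected or that any would be misclassified. The one-patient shift and the 8-15% mortality range are illustrations. The latter also applies survival figures for leptomeningeal disease in general to a trial restricted to ECOG 0-1.

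**What to change.** Reconcile Table 7 footnotes 3 and 7 with sections 6.1.2.7.2, 6.1.2.7.3 and 6.1.2.8.3, so that MRI, CSF and neurologic assessment share one endpoint window that lies wholly after dose 4 and includes week 12. In section 7.2.4, state that:

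- primary response is determined at that assessment;
- a scan taken before dose 4 cannot serve as the endpoint scan;
- the 4-week waiver in 6.1.2.7.3 does not apply to it.

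The same text should say how a first negative CSF in the window is classified when its confirmatory sample falls after week 12.

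The cost is protocol and SAP wording. At most one already-planned scan or CSF sample moves later. Treatment and the sample size of 18 are unchanged.
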